Will pregnant women and/or fetuses (as described in 45 CFR 46 Subpart B) be enrolled in the research?

No

E4. Neonates

Will neonates of uncertain viability or nonviable neonates (as described in 45 CFR 46 Subpart B) be enrolled in the research?

No

E5. Children

Will children be enrolled in the research?

No

Section F: Design/Procedure

F1. Design

Select one category that most adequately describes your research:

z.r) Randomized, Efficacy Study -- Surgical Techniques/Interventions

Discuss the research design including but not limited to such issues as: probability of group assignment, potential for subject to be randomized to placebo group, use of control subjects, etc.

Overview. The goal of the study is to conduct and evaluate a time-limited, Veteran peer-support specialist-led navigation intervention on diabetes-specific outcomes, mental health outcomes, and use VHA or community care in Veterans with DM and clinically significant diabetes-related distress. We will evaluate the outcomes of the intervention in a randomized trial comparing the intervention to usual care. The proposed work is informed by an established and ongoing partnership between VHA researchers and clinicians, individual Veterans, and representatives of Veteran Service Organizations (VSOs)/Community Based Organizations (CBOs) serving Veterans. These key partners have been working together for more than a year, as described above, and will collaborate on all aspects of the research, as detailed below. Study design. This is a single-blind, parallel group, randomized trial of a 3-month peer-navigation intervention for Veterans with DM and elevated levels of diabetes-related distress. Participants will be assigned at random (see below) to the intervention (peer navigation with follow-up) or usual care (print materials and encouragement to continue follow-up with health care providers). Assessment of primary, secondary and intermediate end points will occur preintervention at baseline and postintervention at 3 and 6 months.

Participants. We plan to recruit 218 participants (1:1 allocation) over 31 months (7/month). Central to the design of this trial is the recruitment of Veterans who are VHA users and Veterans who are not. We will screen at our local VHA medical center (MEDVAMC) and established community partnerships, including government agencies, CBOs, and VSOs as described above.

Inclusion Criteria:

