In determining the sample size of 218 needed to recruit for the study, we examined the number of patients needed to have adequate power to detect differences between the intervention and usual care groups using the mean DDS17 score as the primary outcome. The sample size was initially based on testing for a medium effect size ($d = .50$) between the intervention and usual care groups at a single time point, using a two-group t test with a 0.05 2-sided significance level and power of 80%. Because we will assess participants at three time points (baseline, posttreatment, and 6 months), this estimate was then adjusted to account for the correlation among the repeated measurements, using the adjustment factor $[1 + (T-1)\bar{\rho}]/T$, where T is the number of follow-up measurements and $\bar{\rho}$ is the correlation coefficient of the repeated measurement. In our study, $T = 2$ follow-up measurements after baseline, and $\bar{\rho}$ is estimated using the relatively high value of 0.5. The sample size determined for the primary outcome was inflated to account for attrition of 30% at 6 months. In a VHA-funded investigator-initiated grant (Behavioral Activation Therapy for Rural Veterans with Diabetes and Depression; PI: [name]), on which members of the research team are co-investigators, attrition at 6 months was 16.9%. Because this study will include Veterans from VHA and non-VHA settings, we estimated attrition to be somewhat higher than what we

found in the study of patients from VHA settings only. Thus, a sample size of 134 patients would need to be recruited (67 in the intervention group and 67 in usual care) for 80% power to find important differences in the DDS17 measures.

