However, to have power to address the secondary outcomes and because only a portion of the recruited Veterans will have anxiety and depression, we increased the sample size of 134 by 62.7% as described below, resulting in 218 Veterans to be recruited. Although all eligible participants will have diabetes-related distress, we expect depression and anxiety to be prevalent in 25% or more of participating Veterans. Fisher et al. found that 22.5% of those with high diabetes-related distress were clinically depressed. For these secondary outcomes, we initially calculated the sample size based on testing for a large effect size ($d = .80$) between the intervention and usual care groups at a single time point, using a two-group t test with a 0.05 two-sided significance level and power of 80%. Adjusting this to account for correlation among repeated measures results in 18.4 participants per group. Finally, adjustment for 30% attrition at 6 months results in a total needed of 27 per group. Therefore, we need to recruit 218 Veterans, of whom we expect 25% (54) to have anxiety and depression. Thus, we will have 80% power to detect a large effect size of .80 for the secondary outcomes of PHQ-8 and GAD-7. If we based the sample size for the secondary outcomes on detecting a medium effect size of .50, the required sample size of 134 patients would mean increasing the total to 536 patients, a number not feasible for this grant (25% of 536 patients = 134 with anxiety and depression).

In our prior work involving similar recruitment methods, we expect that approximately 7% of those referred to the study from VHA patient databases or community partners will be enrolled in the study (i.e. contact made, interested and eligible for the study). Therefore, we estimate that we will need to attempt to contact approximately 3,114 potential subjects in order to enroll 218 patients in the study.

G2. Data Analysis

Provide a description of your plan for data analysis. State the types of comparisons you plan (e.g. comparison of means, comparison of proportions, regressions, analysis of variance). Which is the PRIMARY comparison/analysis? How will the analyses proposed relate to the primary purposes of your study?

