In examining responses to the Formal Care and Service Utilization questionnaire to determine if iNSPiRED Veterans are more likely to choose VHA or community health care, we will use subsets of the data set. In examining beginning to use care, we will use the subset of participants who did not use VHA services at baseline and completed the 6-month questionnaire. We will determine if each participant did or did not use VHA care at 6 months. A continuity-corrected chi-square test will find any significant differences between the groups in the proportions of users at 6 months. Also, we will run a logistic regression with the outcome of whether or not the Veteran newly used VHA care at 6 months with terms for the intervention, SES, race/ethnicity, and referral source. Then a subset not using community care at baseline will be similarly analyzed.

Exploratory mediator analysis. As noted by Kraemer et al., the mediator must measure change occurring during treatment, must correlate with the intervention, and should have a main or interactive effect on the outcome. The exploratory analysis for examining activation and self-efficacy as possible mediators will include calculation of the correlation between the mediators and treatment. Separate linear models for the primary and secondary outcomes will be run in which the independent variables are the treatment (intervention versus usual care), the potential mediators, and the treatment-by-mediator interactions. Once mediators are identified, a subsequent randomized trial could be designed to help establish if a mediator is indeed a mechanism.

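### The logistic models for newly using VHA or community care are fitted by ordinary maximum likelihood in unsized subsets, so the adjusted odds ratio may be biased away from 1; penalised likelihood on the same terms avoids this cheaply

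*Combined protocol and SAP*

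**What the plan says.** New use of VHA or community programmes or care is part of secondary outcome (d) in Section D. For VHA care, Section G2 (Data Analysis, on the Formal Care and Service Utilization questionnaire) restricts the analysis to "the subset of participants who did not use VHA services at baseline and completed the 6-month questionnaire". It plans two analyses there. The first is a continuity-corrected chi-square test on the proportions using VHA care at 6 months. The second is a logistic regression for having "newly used VHA care at 6 months with terms for the intervention, SES, race/ethnicity, and referral source". Participants not using community care at baseline are then analysed in the same way.

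Earlier in G2, SES is defined as income plus education, and referral source as two categories (MEDVAMC, non-MEDVAMC). The plan does not say how income, education or race/ethnicity are coded. It gives no expected size or event count for either subset, and no method for sparse data. The total in Section G1, "resulting in 218 Veterans to be recruited", was set for DDS17, PHQ-8 and GAD-7, not for these models.

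**The concern.** Ordinary maximum-likelihood logistic regression pushes odds ratios away from 1 when there are few events per coefficient, and some coefficients can become infinite (separation). Both models are fitted in part of the completers with at least five coefficients besides the intercept: treatment, income, education, race/ethnicity and referral source. Categorical coding brings this to about nine or ten.

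The VHA model has a further weakness. The opt-out lists in Sections J1 and J2 consist of patients with a VHA visit in the past year, or in the past three years but not the last one. Few MEDVAMC recruits should therefore be VHA non-users at baseline, and referral source may vary little in that subset.

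The logistic odds ratio is the only effect estimate planned for this outcome. If inflated, it would overstate how far peer navigation draws Veterans into care they were not using.

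**Working it through.** **The plan's own figure (G1).** Per group, n = 2 × ((1.960 + 0.842)/d)² × (1 + 0.5)/2 ÷ (1 − 0.30), where the within-person correlation "is estimated using the relatively high value of 0.5".

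- d = 0.50: 62.8 × 0.75 = 47.1; ÷ 0.70 = 67.3. The plan has 67 per group, 134 in all.
- d = 0.80: 24.5 × 0.75 = 18.4; ÷ 0.70 = 26.3, so 27 per group, 54 in all. The plan takes 54 as 25% of 218 (0.25 × 218 = 54.5), and 134 × 1.627 = 218.

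The total is reproduced. None of these steps concerns new use of care.

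**Events per coefficient.** Completers: 218 × 0.70 = 152.6. The non-user share and the overall new-use rate are assumptions. Events = 152.6 × share × rate.

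| Share | n | New use | Events | Per coefficient (5) | Per coefficient (10) |
|---|---|---|---|---|---|
| 20% | 31 | 20% | 6.1 | 1.2 | 0.6 |
| 30% | 46 | 20% | 9.2 | 1.8 | 0.9 |
| 50% | 76 | 30% | 22.9 | 4.6 | 2.3 |
| 70% | 107 | 50% | 53.4 | 10.7 | 5.3 |

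Only the last row with the leanest coding reaches the usual rule of thumb of 10.

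**Bias, first simulation.** 600 trials per row; true odds ratio 2.5; covariates without effect; 10% of the subset in the rarer referral category. At a control rate of 20% the treated odds are 0.25 × 2.5 = 0.625, a rate of 38.5%; the average is 29.2%, so n = 46 gives 13.4 events. Odds ratios are exponentiated mean log odds ratios. Those for maximum likelihood (ML) omit trials in which the treatment coefficient diverged.

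| n (control rate) | Events | Coefficients | Any infinite | Treatment infinite | ML | Firth, same terms |
|---|---|---|---|---|---|---|
| 31 (20%) | 9.1 | 5 | 48% | 3.5% | 3.05 | 2.50 |
| 31 (20%) | 9.1 | 10 | 90% | 20.5% | 3.44 | 2.68 |
| 46 (20%) | 13.4 | 5 | 28% | 0.5% | 2.91 | 2.47 |
| 46 (20%) | 13.4 | 10 | 74% | 2.0% | 3.58 | 2.55 |
| 76 (20%) | 22.2 | 10 | 45% | 0% | 3.01 | 2.49 |
| 107 (20%) | 31.3 | 10 | 24% | 0% | 2.78 | 2.47 |
| 138 (30%) | 56.4 | 10 | 7% | 0% | 2.75 | 2.53 |

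The inflation does not depend on referral source being lopsided. With that variable split 50:50, n = 46 and a 20% control rate, ML gives 2.98 (5 coefficients) and 3.64 (10).

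**Bias, second simulation.** Nine coefficients, control rates of 20-40%, true odds ratio 2.5. Median ML odds ratio: 4.2 to 5.0 at n = 31, 3.0 to 3.5 at n = 40, 3.1 to 3.4 at n = 60, and 2.6 to 2.9 at n = 80 to 140. Firth on the same terms gave 2.35 to 2.64.

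The two simulations use different summaries, and the first understates the problem in the smallest subset because it drops divergent trials. They agree on direction and on how the bias fades with size.

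**The case against.** The strongest reply is that the documents never say the subsets are small. Size, event rate and coding are all assumed here, and with single-term coding and a large subset the model could be adequate. That stands, and it is why the effect is given as a range.

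A reader might infer that the models will fail, or that the outcome will be left without an interpretable result. The documents do not support this. Most of the separation is in covariate coefficients, and a diverging race/ethnicity or referral-source term does not make the treatment odds ratio infinite. From about 13 events upward, treatment itself diverged in 2.5% of trials or fewer. The chi-square test on the same outcome also does not depend on the covariates. It does not fully fill the gap, because it provides a test and no effect estimate.

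A reader might also infer that the community-care model is equally sparse. Nothing in the plan shows that. If most participants use VHA care, the community-care non-users could be a large group, and the referral-source argument does not carry over. Even for VHA non-users, referral source need not be near constant, because the lapsed patients on the opt-out list may contribute MEDVAMC non-users.

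Finally, it is tempting to conclude that SES and race/ethnicity must be dropped. G2 gives a reason for prespecifying them, and the penalised fit performs well with all of them kept.

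**Conclusion.** The concern holds in limited form. The plan applies ordinary logistic regression with at least five coefficients to subsets of about 153 completers, without sizing them or naming a sparse-data method. Against a true odds ratio of 2.5, the typical estimate would be too high by about 70-100% at n = 31 (4.2/2.5 to 5.0/2.5), 20-40% at n = 40 to 60 (3.0/2.5 to 3.5/2.5), and 4-16% at n = 80 to 140 (2.6/2.5 to 2.9/2.5). These figures rest on the assumed subset sizes, 20-40% new use in usual care, about nine coefficients and covariates grouped into categories. The VHA-non-user model is the more exposed of the two. The point is minor: it affects one secondary outcome and leaves the primary DDS17 analysis untouched.

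**What to change.** In G2, keep intervention, income, education, race/ethnicity and referral source, but state that both new-use models will be fitted by Firth-penalised logistic regression with profile-likelihood confidence intervals. Beside each chi-square test, report the unadjusted risk difference with its 95% confidence interval. It would also help to state the covariate coding and the expected size and number of events in each subset.

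The cost is a few lines of SAP wording, a little more analysis work and slight shrinkage of the estimate. Nothing changes in recruitment or data collection. Settling the method before the data are seen also avoids an improvised choice if a fit separates.

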
Peer coach selection and training. We will recruit two Veterans through referral from partner agencies and the VHA to serve as peer coaches. Recruitment, hiring, and interviewing will be based on the VHA's peer hiring toolkit. Peer coaches will not have other employment relationships with the VHA. Study investigators will provide 40 hours of training that will cover the role of a peer support provider, general principles of self-management, DM self-management, motivational techniques, goal setting, communication, safety issues and boundaries, and tracking and follow-up procedures. Included will be 8 hours of Military Veteran Peer Network Basic training provided by Mental Health America of Houston, which equips peer coaches with frontline intervention tools (e.g. modes of peer support; assessment skills; skills in handling suicide prevention, stress, and addictive behaviors). Peers will also be oriented to VHA and community DM and mental health resources. A study investigator-clinician readily accessible by phone will supervise coaches, meeting with each one at least weekly. Peers will be provided an intervention manual that includes safety guidelines.

Patient assessments will be measured by telephone by an independent evaluator without access to group assignments at baseline, M3 and M6: -Background and Demographics (baseline) -DM-related distress score, as measured using the DDS17 -Summary of Diabetes Self-care Activities Questionnaire (SDSCA) -The Patient Health Questionnaire-8 (PHQ-8) -The Generalized Anxiety Disorder-7 (GAD-7) -Veteran's self-report of use of community-based or VHA resources (baseline and M6) -Patient Activation Measure (PAM-13) -Patient-Reported Outcomes Measurement Information System (PCORI) instruments: Self-Efficacy for Managing Social Interactions, Emotions, and Daily Activities Participants will be asked if they would like to be mailed a summary of the study results after the study is completed.

Exit interview. We will administer a semistructured exit interview at M6 to intervention group participants to elicit patient-level barriers/facilitators to engagement and views on how to improve the intervention. Questions are designed to elicit

brief responses. Responses will be entered verbatim into the database.

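### The mediator model does not carry out the plan's own change-during-treatment criterion: it names no baseline outcome, no baseline mediator and no visit order

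*Combined protocol and SAP*

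**What the plan says.** All references are to the combined protocol and SAP. In section G2, the exploratory mediator paragraph sets three conditions: "the mediator must measure change occurring during treatment, must correlate with the intervention, and should have a main or interactive effect on the outcome". It says the analysis "will include calculation of the correlation between the mediators and treatment". It then describes separate linear models for the primary and secondary outcomes, in which "the independent variables are the treatment (intervention versus usual care), the potential mediators, and the treatment-by-mediator interactions". It closes by saying that "a subsequent randomized trial could be designed to help establish if a mediator is indeed a mechanism".

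The paragraph does not say whether the mediator enters as a level or as a change, which visit supplies the mediator and which the outcome, or what significance threshold applies.

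The data for a tighter specification exist. Section F1 states: "Assessment of primary, secondary and intermediate end points will occur preintervention at baseline and postintervention at 3 and 6 months". Section F2 puts the activation measure, the self-efficacy instruments, the DDS17, the PHQ-8 and the GAD-7 in the baseline, M3 and M6 telephone battery.

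**The concern.** The first criterion asks for change during treatment, but nothing in the listed model makes the mediator a change or places it before the outcome. Veterans with low activation may well have high distress at every visit. A model without baseline terms can pick up that standing association and count it as the mediator's effect on the outcome.

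What is at stake is which of activation and self-efficacy is named as a mediator and so becomes a candidate for a later trial. Coding and visits would also be chosen after the data are seen.

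**Working it through.** **Inputs from the documents.** Recruitment is 218 at 1:1 (F1, G1), with 30% attrition at 6 months and a correlation of 0.5 among repeated measurements (G1). So 218 × 0.70 = 152.6; I use 152, or 76 per arm. The plan gives no figure for the mediator analysis. Its primary sample size does reproduce: 2(1.960 + 0.842)²/0.50² = 62.8; × 0.75 = 47.1; ÷ 0.70 = 67.3 per arm, against 67 stated.

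**Assumptions not in the documents.** Baseline mediator M0 and outcome Y0 have SD 1 and correlation r. M3 = s·M0 + 0.4·group + noise, and Y6 = s·Y0 − 0.5·group + noise. The noises are independent and keep the within-arm SD at 1. The mediator has no effect on the outcome. Each test is two-sided at 5%. Settings (s, r) are (0.5, −0.3), (0.6, −0.4) and (0.7, −0.5); only s = 0.5 has a counterpart in G1.

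**Step 1: mediator term.** The within-arm correlation ρ with Y6 is s²r for the M3 level and s·r(s − 1)/√(2(1 − s)) for M3 − M0. With λ = |ρ|√149/√(1 − ρ²), where 149 = 152 − 3, the chance of significance is Φ(λ − 1.96) + Φ(−λ − 1.96).

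| s, r | ρ, level | significant | ρ, change | significant |
|---|---|---|---|---|
| 0.5, −0.3 | −0.075 | 15% | 0.075 | 15% |
| 0.6, −0.4 | −0.144 | 43% | 0.107 | 26% |
| 0.7, −0.5 | −0.245 | 87% | 0.136 | 39% |

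Simulation of the same model gives about 15% to 86% (level) and 14% to 38% (change).

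**Step 2: add the treatment-mediator link.** For the level, λ = 0.4 × √(76/2) = 2.47, so the link is significant in 69%. For change, the SD is √(2(1 − s)) = 1.00, 0.894, 0.775, giving λ = 2.47, 2.76, 3.18 and 69%, 79%, 89%. Multiplying the two steps:

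- Level: 0.15 × 0.69 = 10%; 0.43 × 0.69 = 30%; 0.87 × 0.69 = 60%. Simulation: about 10% to 59%.
- Change: 0.15 × 0.69 = 10%; 0.26 × 0.79 = 21%; 0.39 × 0.89 = 34%. Simulation: about 10% to 33%.

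**Step 3: no shift in the mediator.** The link is then significant in 5%, so for the level the joint rate is 0.05 × 0.15 = 0.8%, 0.05 × 0.43 = 2.1% and 0.05 × 0.87 = 4.3%: about 1% to 4%.

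**Step 4: baseline terms added.** With M0 and Y0 in the model the partial correlation is zero under these assumptions, and the mediator term returns to about 5%. This depends on independent noise. With a noise correlation of −0.2, λ = 0.2 × √147/√0.96 = 2.47 (147 = 152 − 5), and the adjusted term is still significant in about 70%.

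**Step 5: a different data structure.** Suppose mediator and outcome each have a fixed trait, the traits are correlated, treatment shifts the mediator by 0.5 SD, the mediator-outcome correlation is 0.2 to 0.4, and either the main or the interaction term may count. Joint false rates are then 60% to 87% for the M3 level and 7% to 10% for change. With baseline adjustment they are 11% to 13% at stability 0.8 and 17% to 53% at stability 0.5. With no correlation at all the rate is about 8% to 10%, because two 5% tests give 1 − 0.95² = 9.8% before the link is required.

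**The case against.** **The plan has its own screen.** A reader might infer that a stable baseline correlation is enough by itself for a variable to be declared a mediator. The documents do not support that. The mediator must also correlate with the intervention, and under randomisation a baseline correlation produces no such link except by chance (step 3). This objection stands and limits the point to the case where treatment moves the mediator. That case matters, because the intervention is meant to raise activation and self-efficacy (section C, Significance).

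**Change may be intended.** With a 3-month intervention, the natural reading of the first criterion is change from baseline to M3. On that reading the fixed-trait structure in step 5 shows no excess over the no-correlation rate. Under the other structure the excess remains, because change is itself related to the baseline mediator and baseline outcome is not in the model. The spurious association there is positive: a larger gain in activation goes with more distress. An analyst who checked direction would discount it, but the criteria do not mention direction.

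**The list may not be exhaustive.** The primary-outcome paragraph of G2 makes SES and race/ethnicity a priori covariates in the regression analyses, so they may apply here too. Neither is a baseline outcome or a baseline mediator.

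**The analysis is exploratory.** A reader might infer that a false finding would settle the design of a later trial. The text says only that such a trial could be designed, and it leaves proof of mechanism to that trial.

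**Conclusion.** The concern holds as a minor point. The plan states a change criterion that its listed model does not carry out: mediator coding, visit order, baseline mediator and baseline outcome are all unspecified. If the intervention shifts the mediator, the effect-on-outcome criterion can be met with no mediator effect, in roughly 10% to 59% of trials (M3 level) or 10% to 33% (change score) once the treatment link is also required. If it does not, the rate is about 1% to 4%. These figures are illustrative. They rest on an assumed shift, correlation, stability, 5% threshold and independent follow-up noise, and step 5 shows that they vary with the data structure.

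A reader might also infer that two baseline terms restore the nominal error rate. That is true only when nothing after baseline drives mediator and outcome together, which neither the documents nor randomisation guarantee. No primary or secondary comparison depends on this analysis.

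**What to change.** State in the mediator paragraph of G2 that:

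- the mediator is the M3 value, or the change from baseline to M3, with one chosen in advance;
- the outcome is the M6 value;
- baseline mediator and baseline outcome are covariates, alongside referral source, SES and race/ethnicity;
- the treatment-by-mediator term is kept;
- the visit and threshold for the treatment-mediator link are given;
- results are reported as exploratory, because baseline adjustment does not remove post-baseline confounding.

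An indirect effect with a bootstrap interval is an optional addition, not a correction.

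The cost is a few lines of text and a few model terms, all from data already collected. The small downside is that the model uses only participants with both M3 and M6 data, unless the multiple imputation already planned in G2 is applied.

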Outcomes: Secondary outcomes. Analyses of the secondary clinical outcomes will be similar to those used for the continuous primary outcomes. We will test assumptions of normality and make transformations as needed. We will then run linear regression models separately for each secondary outcome. The models will include terms for the intervention, time period, time-by-period interaction, the a priori SES and race/ethnicity variables, and the referral source. Significant values for the time-by-treatment interaction will indicate that there were significant differences over time in the secondary outcome. In addition, by dichotomizing the outcomes, we will determine whether the groups differed in having or not having clinically significant changes in PHQ-8 and GAD-7 scores. A 5.0-point decrease in the value of PHQ-8 will be considered a minimally clinically important change⁹⁴ and coded as such; decreases of less than 5.0 points from baseline will be coded as not having achieved clinically significant change. For GAD-7, a score of less than 10 will be considered as having clinical improvement, with scores of 10 or higher representing clinically elevated anxiety symptoms. We will test whether the two groups (clinically significant change vs. no clinical change) differed using a logistic regression model in which the dichotomous outcomes are the dependent variable. The independent variables will be those described above for the linear regression models.

For the secondary outcomes of use of printed/web-based resources, health promotion programs, and clinical care, we will run logistic regression analyses of dichotomized variables (i.e., whether or not the patient used printed/web resources, whether or not he/she used health promotion programs, and whether or not he/she used clinical care during the 6-month follow-up). The models will include terms for the intervention, the a priori SES and race/ethnicity variables, and the referral source. Significant values for the treatment term will indicate that there were significant differences between the iNSPiRED and usual care groups.

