Stakeholder quantitative and qualitative data. As part of the mixed methods process evaluation, the lead co-Investigator will analyze quantitative and qualitative responses to the WE-ENACT survey as it is collected (every 6 months) and at study conclusion so that quality of engagement at different stages of the research can be described to provide insight into community engagement at the project level. Responses to open-ended questions (qualitative data) will be used to understand responses to closed-ended questions (quantitative) better and to posit possible explanations for quantitative findings. We do not have a formal hypothesis concerning how domains of engagement will change over time; however, the literature suggests that domains such as trust may vary over time but improve overall. Data collected through the process diary and peer coach weekly reflections will be analyzed in the same manner as is qualitative data from the exit interviews and summarized by the lead co-Investigator and the research team to characterize barriers and facilitators to implementation of the peer navigation and community engagement components of the study from the perspective of peer coaches and other study team members. Findings will be used to inform future studies of implementation and the spread of peer coaching and CBPR interventions to improve access to and engagement in DM self-care strategies.

Missing data. We will conduct sensitivity analyses using tests for data missing completely at random and tests for nonrandom missingness. For nonrandom missing data, the Markov chain Monte Carlo imputation method will be used. We will also follow guidance by Sterne et al. In imputation, we will assess nonnormality of the data and transform variables as needed to approximate normality before imputation and then transform the imputed values back to the original scale. We will attempt to avoid bias in the imputation analyses by including all variables in the substantive analyses and, when computationally feasible, all variables predictive of the missing values and all variables influencing the cause of the missing data, even if they are not of interest in the substantive analysis. We will conduct both complete case analyses and multiple imputation analyses, and if the results differ, we will seek possible reasons and report them publicly. Sensitivity analyses will investigate the robustness of the findings to assumed missing-not-at-random mechanism.

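### The only imputation recipe is for variables that can be made normal, so the yes/no use-of-care outcomes have no suitable method; rounding would attenuate a true odds ratio

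*Combined protocol and SAP*

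**What the plan says.** The method is in section G2, Missing data. It states that "For nonrandom missing data, the Markov chain Monte Carlo imputation method will be used". Its only instruction on distributions is to assess non-normality and "transform variables as needed to approximate normality before imputation and then transform the imputed values back to the original scale". The imputation model is built by "including all variables in the substantive analyses", so treatment arm is in it. On the role of imputation: "We will conduct both complete case analyses and multiple imputation analyses"; differences are to be explained and reported. The paragraph also commits to published imputation guidance.

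For use of printed/web resources, health-promotion programs and clinical care, section G2 (Secondary outcomes) says "we will run logistic regression analyses of dichotomized variables". Section F2 lists the source as "self-report of use of community-based or VHA resources (baseline and M6" only. The analyses of newly used care are limited to participants who "did not use VHA services at baseline and completed the 6-month questionnaire".

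**The concern.** No transformation makes a 0/1 variable normal. A draw from a normal model is a value such as 0.37, which cannot be the outcome of a binary logistic regression. It has to become 0 or 1, and the plan does not say how. Rounding is the obvious route, and it distorts the imputed proportions.

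The gap falls where imputation matters most. The DDS17 analysis is a random coefficient model that already keeps participants with a missed visit. The use-of-care analyses rest on one month 6 report, so a missed call leaves no outcome. These outcomes serve secondary objective d. At stake is the planned comparison of complete-case and imputed results: part of any difference could come from the imputation model and be read as information about the missing data.

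**Working it through.** **How many outcomes are missing.** The plan's attrition figure is confirmed from its own sample size (section G1):

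- Primary: 2 × ((1.960 + 0.842)/0.5)² = 62.79; × 0.75 for repeated measures = 47.09; ÷ 0.70 = 67.3 per group (plan: 67, total 134).
- PHQ-8 and GAD-7: 24.53 × 0.75 = 18.40; ÷ 0.70 = 26.3, rounded up to 27 (plan: 18.4 and 27).

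Missing month 6 outcomes are then 218 × 0.30 = 65.4, or 218 × 0.169 = 36.8 at the earlier study's attrition. The plan gives no figure for imputation bias, so there is none to reproduce.

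**Effect of rounding.** Assume use rates p0 (usual care) and p1 (iNSPiRED), the same share m missing completely at random in each arm, treatment in a normal imputation model, and draws rounded at 0.5. In large samples:

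- pooled residual SD: s = √[(p0(1−p0) + p1(1−p1))/2]
- imputed share in an arm: q = Φ((p − 0.5)/s)
- analysed share: (1−m)p + mq

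Example, 10% vs 20%, m = 0.30: s = √[(0.09 + 0.16)/2] = 0.354. q0 = Φ(−1.131) = 0.129 and q1 = Φ(−0.849) = 0.198. The analysed shares are 0.70 × 0.10 + 0.30 × 0.129 = 0.1087 and 0.70 × 0.20 + 0.30 × 0.198 = 0.1994. The odds ratio is 0.2491/0.1220 = 2.04, against a true 2.25 (9% low).

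| Assumed use | True OR | OR, 30% missing | OR, 16.9% missing |
|---|---|---|---|
| 5% vs 15% | 3.35 | 2.85 (15% low) | 3.06 (9% low) |
| 10% vs 20% | 2.25 | 2.04 (9% low) | 2.13 (5% low) |
| 10% vs 25% | 3.00 | 2.64 (12% low) | 2.78 (7% low) |
| 20% vs 30% | 1.71 | 1.63 (5% low) | 1.67 (3% low) |
| 30% vs 50%, or 50% vs 70% | 2.33 | 2.21 (5% low) | 2.26 (3% low) |
| 80% vs 90% | 2.25 | 2.04 (9% low) | 2.13 (5% low) |

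**Simulation** (N = 20,000, 30% missing at random, treatment and covariates in the imputation model):

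| Assumed use | Full data | Normal, rounded | Logistic imputation |
|---|---|---|---|
| 10% vs 25% | 2.96 | 2.61 | 2.97 |
| 30% vs 50% | 2.33 | 2.23 | 2.35 |
| 50% vs 70% | 2.29 | 2.19 | 2.29 |
| 80% vs 90% | 2.26 | 2.09 | 2.30 |

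Adaptive rounding behaved much like rounding at 0.5.

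**At trial size** (N = 218, 30% missing completely at random, 10% vs 25%), the mean estimates were 3.22 full data, 3.49 complete case, 3.40 logistic imputation and 2.91 rounded normal. Complete-case and logistic results run somewhat high together in sparse data. The rounded result parts from the complete-case one, and that is the comparison the plan intends to interpret.

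**Against the standard error.** For 10% vs 20% with 109 per arm and nothing missing, the SE of the log odds ratio is √[1/(109 × 0.09) + 1/(109 × 0.16)] = 0.40. The shift is ln(2.25/2.04) = 0.10, about a quarter of one SE.

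**Categorical covariates.** With an assumed 15% of a binary covariate missing, normal imputation and rounding left the treatment odds ratio unchanged (2.93 vs 2.93; 2.31 vs 2.31). Only the covariate's own odds ratio moved (2.26 to 2.21; 2.22 to 2.15).

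**The case against.** The strongest reply is that the bias comes from a step the plan does not contain. The text mentions no rounding and never says multivariate normal. Bernoulli draws from the same normal model are almost unbiased when data are missing completely at random (2.96 vs 2.96; 2.35 vs 2.33). Complete-case results are reported alongside, imputation sits within sensitivity analyses, and the cited guidance may cover binary variables. Much of this stands. The normal model is an inference, though the natural one from a transform and back-transform recipe. The attenuation is conditional on rounding. What remains is that the plan specifies no alternative, and reporting both analyses does not help if the imputation itself creates the gap between them.

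Stronger readings that the documents do not support:

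- *A reader might infer that every odds ratio is pulled towards 1.* The direction is not fixed. With 20% use in both arms, q = Φ(−0.75) = 0.227. If 20% are missing under usual care and 40% under iNSPiRED, the analysed shares are 0.2053 and 0.2107, and an odds ratio of 1 becomes 1.03. With the missingness reversed it becomes 0.97.
- *A reader might include newly used VHA or community care.* Those analyses are restricted to month 6 completers, so the outcome is observed by design.
- *A reader might expect the categorical covariates to bias the treatment effect.* The check above shows no such effect.
- *A reader might infer that rare outcomes nearly vanish*, with 5% imputed as 1.9%. That arises only when both arms are at 5%. At 5% vs 15% the pooled variance gives 6.4% in the lower arm.
- *A reader might extend the point to DDS17, PHQ-8 and GAD-7.* No fault is shown there.

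**Conclusion.** The concern holds in limited form. The single recipe described does not fit the three yes/no use-of-care outcomes, and nothing else is specified for them. If imputed values are rounded, a true treatment odds ratio is attenuated by about 5-15% at 30% missing and about 3-9% at 16.9% missing. These figures assume equal missingness by arm, data missing completely at random within arm, and use rates from 5% vs 15% to 80% vs 90%. The simulations with data missing at random agree. The effect is a fraction of a standard error at 218 participants and does not touch the primary analysis. It matters because it would blur the complete-case versus imputed comparison, and because it leaves an analyst's choice open until after the data are seen. This is a worthwhile improvement, not a threat to the trial's main conclusion. It is also separate from whether the missing-at-random assumption is right.

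**What to change.** In section G2, Missing data, state that:

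- the binary use-of-care outcomes are imputed with logistic models within chained equations, with treatment arm included and no rounding;
- any missing income, education or race/ethnicity is imputed with ordinal or multinomial models;
- DDS17, PHQ-8 and GAD-7 keep the present approach for continuous scores, and their dichotomised versions are derived from the imputed scores;
- the newly-used-care analyses stay restricted to 6-month completers and need no imputed outcome.

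The cost is a different option in standard imputation software, with some extra model set-up and convergence checking, mainly where use is rare or nearly universal. Sample size, visits and primary analysis do not change.
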